## **Trial Design:**

This is a phase II, randomized, double-blind, placebo-controlled study to further establish the efficacy and safety and explore dose effects for bermekimab monotherapy in adults with moderate to severe Atopic Dermatitis (AD). Patients will be assessed for study eligibility at the initial screening visit after providing informed consent. Thirty days are allowed in the screening window to complete all screening procedures and randomize the subject. During the screening period, certain treatments will be washed out, as applicable, according to eligibility requirements. Patients who fail initially may be re-screened once based on the investigator discretion but only if inclusion criteria are met at time of re-screening.

The study is approximately 40 weeks (30 day screening period, 32-week treatment period and a 4-week follow-up period) for all subjects.

The primary efficacy endpoint is the percentage of patients achieving  $\geq 75\%$  improvement from baseline in EASI score at week 16. The EASI is a validated measure used in clinical practice and clinical trials to assess the severity and extent of AD. Secondary measures will include Pruritus NRS, Pain NRS, SCORAD, POEM, GISS, DLQI, HADS, BSA and IGA.

Patients who meet the eligibility criteria at screening will be randomized in a 1:1:1 ratio to one of two treatment arms or placebo:

- Arm 1: 800 mg of bermekimab + placebo loading dose (2mL SC injection containing 400 mg of bermekimab and one 2mL SC injection of placebo) at week 0 followed by weekly (qw) subcutaneous (SC) injections of 400 mg bermekimab through week 31
- Arm 2: 800 mg loading dose of bermekimab (2 x 400 mg SC injections) at week 0 followed by subcutaneous (SC) injections of 400 mg bermekimab every other week (q2w) alternating with matching placebo q2w through week 31.
- Arm 3: 4mL loading dose of placebo (2 x 2mL SC injections) at week 0 followed by weekly placebo injections from week 1 through week 15. Patients in Arm 3 will begin to receive weekly (qw) blinded subcutaneous (SC) injections of 400 mg bermekimab beginning at week 16 through week 31.

In order to maintain blinding, all patients will receive two injections at week 0 and 16, followed by weekly injections from week 1 to 31. Additionally, at least one qualified individual will be designated at each study site to perform all preparation and injection of the investigational product. The designated

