Endogenous anti-IL-1 $\alpha$  antibodies are present in 5% to 28% of the general populationx,xi,xii,xiii. No negative correlations with disease have been noted for these individuals. To the contrary, the presence of natural anti-IL-1 $\alpha$  antibodies has been associated with favorable outcomes, both with respect to rheumatoid arthritis and ischemic heart disease. Animal studies also indicate that IL-1 $\alpha$  loss or antagonism does not result in harm. Moreover, the well-tolerated use of other approved biological agents that employ alternative strategies to block IL-1 activity suggest that MABp1's targeting of IL-1 $\alpha$  represents a safe treatment approach.

In previous dermatology studies bermekimab was well tolerated and showed impressive therapeutic activity. The safety data from XBiotech's open label studies: PT044 atopic dermatitis and PT045 hidradenitis suppurativa established good levels of safety and tolerability for 400mg bermekimab (2mL of 200mg/mL) subcutaneous injections and in both studies no safety signals were identified and no study stopping rules were met.

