## **3. STUDY DESIGN AND OBJECTIVES**

This is a phase II, randomized, double-blind, placebo-controlled study to further establish the efficacy and safety and explore dose effects for bermekimab monotherapy in adults with moderate to severe Atopic Dermatitis (AD). Patients will be assessed for study eligibility at the initial screening visit after providing informed consent. Thirty days are allowed in the screening window to complete all screening procedures and randomize the subject. During the screening period, certain treatments will be washed out, as

applicable, according to eligibility requirements. Patients who fail initially may be re-screened once based on the investigator discretion but only if inclusion criteria are met at time of re-screening.

The study is approximately 40 weeks (30 day screening period, 32-week treatment period and a 4-week follow-up period) for all subjects.

Patients who meet the eligibility criteria at screening will be randomized in a 1:1:1 ratio to one of two treatment arms or placebo:

- Arm 1: 800 mg of bermekimab + placebo loading dose (2mL SC injection containing 400 mg of bermekimab and one 2mL SC injection of placebo) at week 0 followed by weekly (qw) subcutaneous (SC) injections of 400 mg bermekimab through week 31
- Arm 2: 800 mg loading dose of bermekimab (2 x 400 mg SC injections) at week 0 followed by subcutaneous (SC) injections of 400 mg bermekimab every other week (q2w) alternating with matching placebo q2w through week 31
- Arm 3: 4mL loading dose of placebo (2 x 2mL SC injections) at week 0 followed by weekly placebo injections from weeks 2 through week 15. Patients in Arm 3 will begin to receive weekly (qw) blinded subcutaneous (SC) injections of 400 mg bermekimab beginning at week 16 through week 31.

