**Visit 1 (Baseline/Week 0/Day 0) (must occur within 30 days of signing informed consent)**

- **At least 45 minutes before injection:** Remove syringe from refrigeration and lay flat; allow to warm to room temperature. Syringe may be held in hand to warm. Do not heat.
- Pre-injection
  - Verify patient still meets all Inclusion/ Exclusion criteria
  - Height, Weight, BMI
  - Patient Diary
  - POEM, HADS, DLQI
  - EASI, GISS, SCORAD, BSA, IGA
  - Vital signs, Urine Pregnancy
  - Urinalysis
  - Blood draw for chemistry, hematology, inflammation markers, PK/ADA, PD (including IL-6), biomarker and research analysis
- Bermekimab/placebo subcutaneous injection (To deliver a loading dose to subjects in the bermekimab groups while maintaining blinding, all subjects will receive two injections)
- Post-injection
  - Adverse event monitoring
  - Concomitant medications/treatments

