 Assessments/procedures should be conducted in the following order: patient reported outcomes, investigator assessments, safety and laboratory assignments, administration of the study drug.																		
 Concomitant medications within 30 days before screening until 7 days after the last administration of the study drug must be recorded for the purpose of drug-drug and drug-disease interaction evaluation and signal detection																		
 Loading Doses: Treatment arm 1: 800 mg loading dose of bermekimab + placebo (one 2mL SC injection containing 400 mg of bermekimab and one 2mL SC injection of placebo) at week 0; Treatment arm 2: 800 mg loading dose of bermekimab (2 x 2mL SC injections each containing 400 mg of bermekimab) at week 0; Arm 3: 4 mL loading dose of placebo (2 x 2mL SC injections of placebo) at week 0.																		
 Patients in Arm 3 will begin to receive active bermekimab therapy at visit 17 (week 16). Patients in all arms will remain blinded through end of study.																		

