### 1.2. Trial Design

This is a phase II, randomized, double-blind, placebo-controlled study to further establish the efficacy, safety, PK, and explore dose effects for bermekimab monotherapy in adults with moderate to severe Atopic Dermatitis (AD). The participant population will comprise men and women who have had chronic atopic dermatitis present for at least 3 years. The study is approximately 40 weeks (30 day screening period, 32-week treatment period and a 4-week follow-up period) for all subjects.

A diagram of the study design ([Figure 1](#)) is provided below, approximately 90 patients who meet the eligibility criteria at screening will be randomized in a 1:1:1 ratio to one of two active treatment arms or placebo:

- Arm 1: 400 mg loading dose of bermekimab (2mL SC injection containing 400 mg of bermekimab and one 2mL SC injection of placebo) at Week 0 followed by weekly (qw) subcutaneous (SC) injections of 400 mg bermekimab through Week 31
- Arm 2: 800 mg loading dose of bermekimab (2 x 400 mg SC injections) at Week 0 followed by subcutaneous (SC) injections of 400 mg bermekimab every other week (q2w) alternating with matching placebo q2w through Week 31.

- Arm 3: 4mL loading dose of placebo (2 x 2mL SC injections) at Week 0 followed by weekly placebo injections from Week 1 through Week 15. Patients in Arm 3 will begin to receive weekly (qw) blinded subcutaneous (SC) injections of 400 mg bermekimab beginning at Week 16 through Week 31.

Patients will be monitored at a follow up visit (week 36) for safety and clinical assessments after completing the 32 week treatment period.

Efficacy assessments include Eczema Area and Severity Index Score (EASI) score, Itch Numerical Rating Scale (NRS), Pain NRS, Severity Scoring of Atopic Dermatitis (SCORAD), Patient Oriented Eczema Measure (POEM), Global Individual Signs Score (GISS), Dermatology Life Quality Index (DLQI), Hospital Anxiety Depression Scale (HADS), Body Surface Area (BSA) and Investigator's Global Assessment (IGA) will be performed according to the Study Calendars (Section 5.2 of the protocol).

Blood samples will be collected for laboratory testing including chemistry, hematology, inflammation markers, bermekimab concentration (PK), PD marker(s), and anti-drug antibody (ADA).

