## 4.4. Extent of Exposure

The exposure data will be summarized through Week 16 and Week 36. The number and percentage of participants who receive study agent will be summarized by treatment group for the safety analysis set. Descriptive statistics will be presented for the following parameters:

- Number of administrations
- Cumulative total dose

In addition, the average exposure (number of administrations) and average duration of follow-up (weeks) will also be summarized by treatment group in the safety tables through different study time periods.

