#### 7.1.1. Bermekimab Concentrations

Bermekimab concentrations will be summarized using descriptive statistics, including n, arithmetic mean, SD, coefficient of variation (%CV), median, interquartile range, range (minimum and maximum), by treatment group at each PK sampling time where appropriate. PK data may be displayed graphically. The following analyses will be performed as appropriate:

- Summary of bermekimab concentrations at each visit by treatment group

- Proportion of participants without detectable bermekimab concentration (below the lower limit of quantification) at each visit by treatment group
- Summary of bermekimab concentrations at each visit by treatment group and baseline body weight (quartiles). Other covariates may also be applied.
- Summary of bermekimab concentrations at each visit by treatment group and baseline EASI severity.
- Plot of mean (SD) bermekimab concentrations over time by treatment group
- Plot of median (IQ) bermekimab concentrations over time by treatment group

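### The protocol labels Arm 1's Week 0 dose 800 mg three times, but the syringes it lists hold 400 mg, which is the SAP's figure

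*Protocol*

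**What the plan says.** Four places describe Arm 1 at Week 0:

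- Protocol synopsis, Trial Design: "800 mg of bermekimab + placebo loading dose (2mL SC injection containing 400 mg of bermekimab and one 2mL SC injection of placebo".
- Protocol section 3: "Arm 1: 800 mg of bermekimab + placebo loading dose", followed by the same one active and one placebo syringe.
- Protocol 5.2.1, footnote 6: "Treatment arm 1: 800 mg loading dose of bermekimab + placebo (one 2mL SC injection containing 400 mg of bermekimab", again with one placebo syringe.
- SAP 1.2: "Arm 1: 400 mg loading dose of bermekimab (2mL SC injection containing 400 mg of bermekimab", plus one placebo syringe.

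All four list identical injections. Three label them 800 mg and one labels them 400 mg. Arm 2 is labelled 800 mg throughout and is given two active 400 mg injections.

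The Visit 1 procedures in protocol 5.2 explain the two injections as follows: "To deliver a loading dose to subjects in the bermekimab groups while maintaining blinding, all subjects will receive two injections".

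Two further differences concern the same dosing descriptions:

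- **Arm 3 placebo start.** Protocol section 3 starts Arm 3's weekly placebo at Week 2. The synopsis and SAP 1.2 say Week 1. The paragraph after the arm list in section 3 has every patient injected weekly from Week 1. The Visit 2 procedures and the calendar show a Week 1 injection without separating arms.
- **Week 16 injections.** The synopsis and section 3 have all patients receive two injections at Week 16 as well as at Week 0. SAP 1.5.2 mentions two only at Week 0. Visit 17, calendar footnote 7 and the arm descriptions do not state a second Week 16 injection or what it would contain.

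**The concern.** Protocol 10.1 names Arm 1 versus placebo as the primary comparison, and the trial also aims to explore how dose affects response. The label and the contents imply different first doses for Arm 1, and so different starting contrasts between the two active regimens.

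Three parts of the analysis use the Week 0 dose:

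- **Exposure.** SAP 4.4 summarises "Cumulative total dose".
- **PK.** SAP 7.1.1 plans a "Summary of bermekimab concentrations at each visit by treatment group". At Visit 2 blood is drawn before that day's injection, so the Week 1 concentration follows the Week 0 dose alone.
- **Deviation rules.** SAP 4.3 and 4.5 count incorrect doses. SAP 7.1.1.1 removes a patient's by-visit PK data from the point of an incomplete or incorrect dose. At Week 0 these rules need a single reference dose. Measured against the 800 mg label, every Arm 1 patient who received the listed syringes would count as under-dosed from the first visit.

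On the Arm 3 start week, if section 3's arm list were followed, only placebo patients would have no injection at Week 1. That would put the blind at risk, although the visit itself would still take place. The Week 16 difference does not unblind, because each wording treats all arms alike, but it leaves the number and contents of the injections unclear.

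**Working it through.** **Inputs.** The drug product is 200 mg/mL (protocol 2.2). An active injection is described as "400mg bermekimab (2mL of 200mg/mL) subcutaneous injections" (protocol 1.2). Syringe lists are from the four places above. Weekly dosing runs to Week 31. About 90 patients are randomised 1:1:1, so 90 / 3 = 30 per arm.

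**Week 0 dose** = active syringes × 2 mL × 200 mg/mL + placebo syringes × 0 mg.

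| Arm | Listed syringes | Sum | Protocol label | SAP label |
|---|---|---|---|---|
| 1 | 1 active + 1 placebo | 400 + 0 = 400 mg | 800 mg | 400 mg |
| 2 | 2 active | 2 × 400 = 800 mg | 800 mg | 800 mg |

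The Arm 2 label reproduces. The protocol's Arm 1 label does not: it exceeds the listed contents by 400 mg, a factor of 2.

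**Dose before the Week 1 sample, Arm 1 : Arm 2.** By contents it is 400:800 = 0.5. By label it is 800:800 = 1.0.

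**Arm 1 cumulative dose, full compliance.**

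- Weeks 1-15: 15 × 400 = 6,000 mg. Adding Week 0 gives 6,400 or 6,800 mg, a difference of 400 / 6,400 = 6.25%.
- Weeks 1-31: 31 × 400 = 12,400 mg. Adding Week 0 gives 12,800 or 13,200 mg, a difference of 400 / 12,800 = 3.1%. This assumes any second Week 16 syringe is placebo for Arm 1. If it were active, each total rises by 400 mg, so the full range is 12,800 to 13,600 mg.

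**Injections per completer.** SAP 1.5.2: 2 at Week 0 + 31 at Weeks 1-31 = 33. Protocol wording: 33 + 1 more at Week 16 = 34.

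**Sample size.** Rates of 60% against 20% at two-sided 0.05 give 23 per group, with power 0.812. This reproduces the plan's 23 per group for approximately 80% power, and the dose label does not enter the calculation.

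**The case against.** The strongest reply is that the injections never vary: every description gives Arm 1 one active and one placebo syringe. A site that follows the list would treat all patients alike, and only the label differs. The SAP, which governs the analysis, has label and contents in agreement. Cumulative dose and concentration are summaries of recorded and measured data, so a wrong label does not alter them if administration is recorded correctly. Comparison of the two active regimens is descriptive, since the tests are each against placebo.

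Much of this stands. Misdosing is possible but not shown, and the pharmacy manual is not among the documents. The Visit 1 wording is weak evidence either way: it speaks of a loading dose for both bermekimab groups, but the SAP also uses that term for a 400 mg dose equal to Arm 1's weekly dose. The Arm 3 start week is a single outlier against several consistent statements. SAP 1.5.2 omits a second Week 16 injection rather than denying it. Neither of these two would carry the point alone.

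The reply does not remove the conflict. The label cannot be a combined amount, because placebo contributes no milligrams. Footnote 6 gives Arms 1 and 2 the same 800 mg label over different contents. The error occurs three times in the governing document, and the SAP does not present its 400 mg as a departure from the protocol. Correct recording also does not tell the analyst which Week 0 dose counts as correct under the deviation and PK exclusion rules.

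**Conclusion.** The concern holds. The protocol's Arm 1 Week 0 label is twice the sum of the syringes listed beside it and conflicts with the SAP. It affects one dose in about 30 patients in the primary-comparison arm. The planned Arm 1 to Arm 2 ratio before the Week 1 sample is 0.5 or 1.0, and Arm 1's planned cumulative dose for Weeks 0-15 differs by 6.25%. The cumulative figures assume full compliance. Those for Weeks 0-31 also depend on what any second Week 16 syringe contains. There is no effect on sample size, power or the tests against placebo as planned. The two lesser mismatches are real but secondary.

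**What to change.** The sponsor must reconcile these passages so that:

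1. Arm 1's Week 0 milligram label and its syringe list agree, whichever of the two is changed.
2. Arm 3's placebo start week is the same throughout.
3. The number of Week 16 injections, and their contents by arm, are stated once and repeated consistently.

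Matching wording is needed in the protocol synopsis, section 3, the Visit 1, 2 and 17 procedures, calendar footnotes 6 and 7, and SAP 1.2 and 1.5.2. The SAP's incorrect-dose and PK exclusion rules should then refer to the reconciled Week 0 dose. No view is taken here on which dose or schedule is intended.

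The cost is a protocol clarification and corresponding SAP text, with no extra patients or procedures.

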### **Procedures and Assessments:**

Multiple parameters will be collected during the study to evaluate the efficacy of bermekimab, including measures of AD severity, and patient-reported measures of AD symptoms and quality of life.

The safety of bermekimab in this population will be assessed by evaluating treatment emergent adverse events (TEAEs), vital signs, thorough physical examination, detailed medical history, electrocardiograms (ECGs), and clinical laboratory testing. Concomitant medications and procedures will be collected from time of informed consent to the end of study. Safety data will be reviewed on an ongoing basis by the sponsor.

Blood samples will be collected for laboratory testing including chemistry, hematology, inflammation markers, bermekimab concentration (PK), PD marker(s), anti-drug antibody (ADA) and research analysis etc. at pre-determined time points.

**Figure 1. Study Flow Diagram**

	Screening	Treatment Period			Follow-up
		Baseline	Weekly Dosing	Endpoint Assessment	
Visit (V)		V1	V2 to V32	V33	V34
Week (W)	D -30 to -1	W0	W1 to W31	W32	W36
Day (D)		D0	D7 to D217	D224	D252

**Inclusion Criteria:**

**No waivers/exemptions will be granted for protocol inclusion/exclusion criteria.**

Subjects are included in the study if they meet all of the following criteria:

- Written informed consent provided by the patient.
- Male or female, at least 18 years.
- Willing and able to attend all clinic visits and comply with study-related procedures.
- Is able to understand and complete study-related questionnaires.
- Chronic atopic dermatitis present for at least 3 years.
- EASI score  $\geq 16$  at screening and baseline visits.
- IGA score  $\geq 3$  at screening and baseline visits.

- Baseline pruritis numerical rating scale average score for maximum intensity of at least 3, based on the average of daily pruritis numerical rating scale scores for maximum itch intensity reported during the 7 days prior to randomization.
- Has applied a stable dose of topical moisturizer twice daily for at least 7 consecutive days immediately prior to the baseline visit and is willing to continue this regimen on a daily basis for the duration of the study.
- $\geq 10\%$  body surface area (BSA) of AD involvement at screening and baseline visits.
- Documented recent history (within 6 months prior to screening) of inadequate response to treatment with topical medications, or patients for whom topical treatments are medically inadvisable (because of important side effects or safety risks).
  - a) Inadequate response is defined as failure to achieve and maintain remission or a low disease activity state (comparable to an IGA score of 0-2), despite treatment with a daily regimen of topical corticosteroids of medium to higher potency (with or without topical calcineurin inhibitors as appropriate), applied for at least 28 days or for the maximum duration recommended by the product prescribing information, whichever is shorter.
  - b) Patients with documented systemic treatment for atopic dermatitis in the preceding 6 months are also considered to be inadequate responders to topical treatments and are potentially eligible for treatment with bermekimab, after appropriate washout.
  - c) Important side effects or risks are those that outweigh the potential treatment benefits, and include: intolerance to treatment, hypersensitivity reactions, significant skin atrophy, and adverse systemic effects.
  - d) Acceptable documentation includes contemporaneous chart notes that record topical medication prescription and treatment outcome, or investigator documentation based on communication with the patient's treating physician.

**Exclusion Criteria:**

Subjects with ANY of the following will be excluded from the study:

- Age below 18 years as the current study is evaluating bermekimab in adult patients only.
- Subject has been treated for AD with any investigational drug of chemical or biologic nature within a minimum of 30 days or 5 half-lives (whichever is longer) of the drug prior to baseline.
- Treatment with bermekimab at any time in the past.
- Treatment with immunosuppressive/immunomodulatory drugs or phototherapy for atopic

dermatitis within 4 weeks of baseline, or any condition that, in the opinion of the investigator, is likely to require such treatment(s) during the first 4 weeks of study treatment.

- Treatment with topical corticosteroids or topical calcineurin inhibitors for the treatment of AD within 14 days prior to baseline].
- Treatment with biologics as follows:
  - a) Any cell-depleting agents including, but not limited to, rituximab, within 5 half-lives (if known) or 30 days prior to baseline visit, or until lymphocyte count returns to normal, whichever is longer.
  - b) Other biologics: within 5 half-lives (if known) or 30 days prior to baseline visit, whichever is longer
- Initiation of treatment of atopic dermatitis with prescription moisturizers or moisturizers containing additives such as ceramide, hyaluronic acid, urea, or filaggrin degradation products during the screening period (patients may continue to use stable doses of such moisturizers if initiated before the screening visit).
- Regular use (more than 2 visits per week) of a tanning booth/parlor within 4 weeks of the screening visit.
- Planned or anticipated use of any prohibited medications and procedures during study treatment.
- Treatment with a live (attenuated) vaccine within 30 days prior to the screening visit.
- Active chronic or acute infection requiring treatment with systemic antibiotics, antivirals, antiparasitics, antiprotozoals, or antifungals within 2 weeks prior to the baseline visit, or superficial skin infections within 1 week prior to the baseline visit. NOTE: patients may be rescreened after infection resolves.
- Known or suspected history of immunosuppression, including history of invasive opportunistic infections (e.g., tuberculosis, histoplasmosis, listeriosis, coccidioidomycosis, pneumocystis, aspergillosis) despite infection resolution; or unusually frequent, recurrent, or prolonged infections, per investigator judgment.
- History of human immunodeficiency virus (HIV) infection or positive HIV serology at screening.
- Positive for hepatitis B surface antigen, hepatitis B core antibody, or hepatitis C antibody at the screening visit.
- At baseline, presence of any conditions listed as criteria for study drug discontinuation.
- Presence of skin comorbidities that may interfere with study assessments.
- History of malignancy within 5 years before the screening visit, except completely treated in situ carcinoma of the cervix, and completely treated and resolved non-metastatic squamous or basal cell carcinoma of the skin.

- Severe concomitant illness(es) that, in the investigator's judgment, would adversely affect the patient's participation in the study. Examples include, but are not limited to, patients with short life expectancy, patients with uncontrolled diabetes (HbA1c  $\geq$  9%), patients with cardiovascular conditions (eg, stage III or IV cardiac failure according to the New York Heart Association classification), severe renal conditions (eg, patients on dialysis), hepato-biliary conditions (eg, Child-Pugh class B or C), neurological conditions (eg, demyelinating diseases), active major autoimmune diseases (eg, lupus, inflammatory bowel disease, rheumatoid arthritis, etc.), other severe endocrinological, gastrointestinal, metabolic, pulmonary or lymphatic diseases. The specific justification for patients excluded under this criterion will be noted in study documents (chart notes, case report forms [CRFs], etc.).
- Planned or anticipated major surgical procedure during the patient's participation in this study.
- Patient or immediate family member is part of the current clinical investigational team.
- Pregnant or breastfeeding women, or women planning to become pregnant or breastfeed during the study.
- Women unwilling to use adequate birth control, if of reproductive potential and sexually active. Adequate birth control is defined as consistent practice of an effective and accepted method of contraception throughout the duration of the study and for 120 days after the last dose of study drug. These methods include oral contraceptives (stable use for more than 3 months before Screening), intrauterine device (IUD), hormonal contraceptives such as Depo-Provera (stable use for more than 3 months before Screening), Implanon implants (stable use for more than 3 months before Screening), double barrier contraception such as condom or diaphragm used with contraceptive sponge, foam, or jelly. For men participating in the study, unwillingness of sexual partner to use any of the above contraception methods.
- History of severe allergic or anaphylactic reactions to monoclonal antibodies.
- Any other medical or psychological condition (including relevant laboratory abnormalities at screening) that, in the opinion the investigator, may suggest a new and/or insufficiently understood disease, may present an unreasonable risk to the study patient as a result of his/her participation in the study, may make patient's participation unreliable, or may interfere with study assessments. The specific justification for patients excluded under this criterion will be noted in study documents (chart notes, case report forms, etc.)

